### 10.2.5 Visits 5 to 15 (Visits each 30 Days; V5 $\pm$ 3 days, V6 to V15 $\pm$ 7 days)

Subjects will continue to be monitored for safety and effectiveness at one-month intervals. On and after **Day 90**, subjects are eligible to exit the study once their GLS score at maximum frown has returned to Baseline (Investigator assessment). Subjects will return for monthly assessments until they reach their Baseline GLS score (Investigator assessment). Assessment procedures include:

- Brow Area Photography
- Effectiveness Evaluations Investigator (Blinded Evaluator)
  - GLS (max frown)
  - GAIS
- Effectiveness Evaluations Subject
  - GLS (max frown)
  - GAIS
  - Subject Satisfaction
  - Clinical Interview (Visit 5; Day 30 only) (Section 10.3.4)
- Safety Assessments Investigator (Blinded Evaluator)
  - Directed Questionnaire
  - Directed Review of Systems
  - Vital Signs
  - Physical Exam
  - Concomitant Medications
  - Adverse Events

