7.6. Sample Size Considerations

This study is not powered for inferential analyses. Approximately 150 subjects will be randomized to the study, 50 subjects in each of the three treatment arms; 20U onabotulinumtoxinA, 20U prabotulinumtoxinA and 40U prabotulinumtoxinA. Assuming 50 subjects per treatment group, exponential distributions for failure and censoring times, a median duration of effect of 4 months in the reference group, and an annual censoring rate of 10%, the study will have 80% power to detect a hazard ratio of 0.47 based on a one-sided hypothesis test of the primary effectiveness endpoint with alpha = 0.025. As such, it is the opinion of the study Sponsor that 50 subjects per group (total sample size n=150) will be sufficient to address the objectives of this study.

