7.7. General Considerations

Data will be listed by subject number. Data will be summarized by treatment and study visit, where applicable. For categorical parameters, the number and percentage of subjects/observations in each category will be presented; percentages will be based on the number of subjects in the relevant analysis population in each treatment group. For continuous parameters, descriptive statistics will include n (number of subjects or observations), mean, standard deviation, median, and range. A full description of the statistical methods planned for this study will be provided in the Statistical Analysis Plan (SAP). All programs for data output and analyses will be written in SAS version 9.4 or higher (SAS Institute, Inc., Cary, NC).

Missing Values: For the mITT analysis of primary, secondary, tertiary, and exploratory duration of effectiveness endpoints, in the case of a missed visit, subjects will be considered to have returned to Baseline if they are confirmed to have returned to Baseline at the next non-missed visit. Subjects will be considered to have to have returned to Baseline if they fail to attend 2 consecutive visits or drop out of the study. For missing observations for exploratory endpoints other than duration of effect data will be analyzed as observed without imputation.

Discontinuation and Drop-Outs: Dropouts will not be replaced. Subject disposition will summarize the number of subjects who were randomized and who discontinued from the study (including reasons for discontinuation).

Interim Analysis: An interim analysis will be conducted when >90% of subjects have completed Visit 8 (Day 120) to evaluate response to exposure (efficacy, duration) and adverse events. For assessment of the primary effectiveness endpoint, 95% CIs will be presented but statistical analyses will not be conducted and a statistical penalty for the final analysis will not be employed. While data by treatment group will be presented, individual subjects will not be unblinded.

Poolability of Investigative Sites: Data from all investigative sites will be pooled based on the assumption of clinical comparability: the same protocol will be used for all sites, all sites will be monitored for protocol compliance, and the same data collection instrument and methodology will be used across all sites.

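### Counted over all randomized subjects, the interim trigger (more than 90% through Visit 8) is out of reach on the plan's own assumptions, because subjects who exit on return to Baseline by Day 90 have no Visit 8

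*SAP*

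**What the plan says.** **Trigger.** SAP 7.7, repeated in Protocol 12.8: "An interim analysis will be conducted when >90% of subjects have completed Visit 8 (Day 120". The denominator is not defined. The look covers efficacy, duration and adverse events by treatment group. The primary endpoint gets 95% confidence intervals, with no statistical testing and no penalty at the final analysis.

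**Exit.** Protocol 4.1, SAP 2.1 and footnote 3 of both schedules have the subject leave on return to Baseline, with no minimum day. Protocol 10.2.5 sets a floor of Day 90, from which "subjects are eligible to exit the study once their GLS score at maximum frown has returned to Baseline (Investigator assessment". It also says monthly assessments run until Baseline is reached. Under Protocol 10.2.6 the assessment at exit is the Final Visit.

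**Planning assumptions (SAP 7.6).** "Approximately 150 subjects will be randomized to the study, 50 subjects in each of the three treatment arms"; "exponential distributions for failure and censoring times"; "a median duration of effect of 4 months in the reference group"; 10% annual censoring; and "the study will have 80% power to detect a hazard ratio of 0.47".

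**Analysis rules (SAP 7.7).** Missing data for exploratory endpoints other than duration are left unimputed and analysed on what was observed. A general sentence in the same section bases percentages on the analysis population, but the responder-rate shells (SAP Tables 14.3.3.3.1 and 14.3.3.3.2) carry a separate N at each visit.

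**The concern.** Visits 5, 6, 7 and 8 are Days 30, 60, 90 and 120. A subject who exits on return to Baseline at or before Visit 7 therefore never has a Visit 8. For more than 90% of randomized subjects to complete it, fewer than 10% may have returned or dropped out beforehand. With a planned reference median of 4 months, far more than 10% should be back by Day 90.

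Two things are at stake. First, a trigger that does not work on its plain reading leaves the sponsor to choose the date of a by-arm look. Second, if the Day 120 tables use only subjects still attending, they describe subjects selected for not having lost effect by Day 90, and the selection is stronger in the arms with shorter effect.

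**Working it through.** **The plan's own figure.** The plan states no figure for the share reaching Visit 8. The figure that rests on the same inputs is the 80% power. With 12 months of follow-up, expected events are 42.2 (20U) + 29.8 (40U), or 72.1 before rounding.
- Schoenfeld: √72.1/2 × |ln 0.47| − 1.96 = 1.245, power 89.3%.
- Freedman: √72.1 × 0.53/1.47 − 1.96 = 1.10, power 86.5%.

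So 80% is not reproduced this way. SAP 7.6 gives no accrual or follow-up time, and two variants come close: Freedman with about 8 months of follow-up (79.6%), or with 0.025 taken as two-sided (79.4%). This is a separate matter, and nothing below depends on it.

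**Threshold.** 0.90 × 150 = 135, so more than 90% means at least 136.

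**Share still on effect after Day 90** (month of 30 days; onabotulinumtoxinA assumed equal to the reference, since its median is not stated):
- 20U arms: exp(−ln 2 × 3/4) = 59.5%, so 40.5% have returned.
- 40U arm: 0.595^0.47 = 78.3%, so 21.7% have returned.
- Average: (2 × 59.5 + 78.3)/3 = 65.7%, or 98.6 of 150. About 51 subjects never have a Visit 8.
- Dropout to Day 120: 0.9^(120/365) = 0.966, and 65.7% × 0.966 = 63.5%, or 95.3 of 150.
- Chance of at least 136 of 150, before dropout: about 6 × 10⁻¹³.

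**Sensitivity, before dropout unless stated:**
- 4 months as 121.75 days: 66.1%, and 63.9% after dropout.
- Visit 7 at Day 83 or Day 97 (window limits): 67.9% or 63.7%.
- No treatment difference: 59.5%.
- Hazard ratio 0.47 in the onabotulinumtoxinA arm as well: 72.0%. In all three arms: 78.3%, with a chance of about 5 × 10⁻⁵ of reaching 136.
- Exponential median, common to the arms, that leaves 90% on effect at Day 90: 90 × ln 2/(−ln 0.9) = 592 days. With dropout to Day 90 (0.9^(90/365) = 0.974): 90 × ln 2/(−ln(0.9/0.974)), about 786 days.

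**Times clustered more tightly.** The shapes k are assumptions. S(90) = exp(−ln 2 × (90/121.75)^k), raised to the power 0.47 for 40U:

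| Shape k | 20U | 40U | Average | After dropout to Day 90 | After dropout to Day 120 |
|---|---|---|---|---|---|
| 1 | 60% | 79% | 66% | 64% | 64% |
| 2 | 69% | 84% | 74% | 72% | 71% |
| 3 | 76% | 88% | 80% | 78% | 77% |
| 4 | 81% | 91% | 84% | 82% | 82% |
| 6 | 89% | 95% | 91% | 89% | 88% |
| 8 | 94% | 97% | 95% | 93% | 92% |

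The trigger comes into reach only at a shape of about 6 before dropout, and between 6 and 8 after it.

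**Day 120 response rates.** Take not yet returned to Baseline as the response (a GLS improvement of at least 1 point), with exponential times and 121.75 days:
- All subjects: 0.5^(120/121.75) = 51% (20U); raised to the power 0.47, 73% (40U). Difference 22 points.
- Only those still present after Day 90: 0.5^(30/121.75) = 84% (20U); raised to the power 0.47, 92% (40U). Difference 8 points.

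**The case against.** **The denominator is open.** The text does not say randomized subjects. Protocol 11.2 ties completion to applicable visits, and SAP Table 14.1.2 lists subjects followed up to return to Baseline as completing the study. One can argue that Visit 8 does not apply to someone who has already exited. If such exits count, only dropout works against the trigger, and retention to Day 120 is 96.6%. This stands: a reader might infer that the interim can never take place, and the documents do not support that without the all-randomized denominator. But those places define completion of the study, not of Visit 8, so they do not supply the missing rule.

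**Duration is not biased.** A reader might also infer that the interim overstates duration of effect. It does not follow. The trigger fixes when data are cut, not who is analysed. Duration is estimated by Kaplan-Meier in the mITT population (SAP 7.1 and 7.5.1), where a return by Day 90 is an event. Nothing restricts that estimate to subjects who completed Visit 8.

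**Consequences are limited.** No test, stopping rule or adaptation is attached, and the trial is declared not powered for inference. This stands too: the documents give no ground for inferring harm to the final duration analysis or its error rate.

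**The response-rate problem is not caused by the trigger.** That is correct. The observed-data rule acts at every late visit, and rewording the trigger alone would not cure it. The general sentence on percentages in SAP 7.7 could be read as keeping the full denominator, but the specific missing-data rule and the per-visit N point the other way. The text needs to say which applies.

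**Conclusion.** The point holds as a defect of wording with a practical consequence. With all randomized subjects as the denominator, about 64% to 66% can reach Visit 8 against a requirement of more than 90%. This rests on exponential times, a 4-month reference median, hazard ratio 0.47 for 40U and onabotulinumtoxinA equal to the reference. Assumed Weibull shapes 2 to 6 give about 72% to 89% with dropout counted to Day 90. Only very tight clustering of return times, or a different denominator, makes the trigger reachable.

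The two exit rules differ, but a subject who leaves on return by Day 90 has no Visit 8 under either, so the result does not turn on which applies.

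The effect on results is confined to visit-level response rates. On the plan's assumptions, Day 120 figures of about 51% and 73% would read about 84% and 92%. Severity is minor to moderate.

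**What to change.** 1. In SAP 7.7 and Protocol 12.8, state the trigger as: *more than 90% of randomized subjects have completed Visit 8 (Day 120) or exited the study before it (return to Baseline or discontinuation)*.
2. State that Day 120 response rates keep in the denominator mITT subjects who exited earlier after return to Baseline, counted as GLS non-responders. For Investigator GLS this follows from the definition: a subject back at a Baseline score of 2 or 3 meets none of the responder criteria. For subject-rated GLS it is a convention, which the SAP should name as such.
3. Reconcile the exit wording of Protocol 4.1 and SAP 2.1 (exit at any return) with Protocol 10.2.5 (eligible to exit on and after Day 90).
4. If the interim has already been run, report the denominator and data cut that were used.

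The cost is a few sentences in the two documents. No visits, data or subjects are added.

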14.1 Subject Disposition

Table 14.1.1 Enrollment

Site	Screened	Screen Failures	Randomized	PP	ITT	SAFT
01	XX	XX	XX	XX	XX	XX
02	XX	XX	XX	XX	XX	xx
03	XX	XX	XX	XX	XX	XX
04	XX	XX	XX	XX	XX	xx
05	XX	XX	XX	XX	XX	XX
All sites	XX	XX	XX	XX	XX	XX

Number of subjects

Table 14.1.2 Subject Discontinuations with Primary Reason

Study Exit		PraB 40 (n = xx)	OnaB 20 (n = xx)	PraB 20 (n = xx)
Completion of Study	N	XX	XX	XX
	Completed up to return to BL	xx (xx.x%)	xx (xx.x%)	xx (xx.x%)
Primary Reason for d/c* prior	N	xx (xx.x%)	XX	XX
to return to BL	Adverse Event	xx (xx.x%)	xx (xx.x%)	xx (xx.x%)
	Lost to follow- up	xx (xx.x%)	xx (xx.x%)	xx(xx.x%)
	Withdrew consent	xx (xx.x%)	xx (xx.x%)	xx (xx.x%)
	Protocol violation	xx (xx.x%)	xx (xx.x%)	xx (xx.x%)
	Investigator Decision		xx (xx.x%)	xx (xx.x%)
	Other		xx (xx.x%)	xx (xx.x%)

Number of subjects (% in parenthesis). *d/c= discontinuation

Table 14.1.3 Listing of Subject Discontinuations

Subject	Treatment	Gender*	Age	Last Visit	Primary Reason for
Number	Group				Discontinuation
##-###	PraB 40	M/F	XX	V#	xxxxxxxxxxxxxxxx
##-###	PraB 20	M/F	XX	V#	xxxxxxxxxxxxxxx
##-###	OnaB 20	M/F	XX	V#	xxxxxxxxxxxxxxxx
##-###	OnaB 20	M/F	XX	V#	xxxxxxxxxxxxxxx
##-###	PraB 40	M/F	XX	V#	xxxxxxxxxxxxxxxx
##-###	PraB 20	M/F	XX	V#	xxxxxxxxxxxxxxx
##-###	PraB 40	M/F	XX	V#	XXXXXXXXXXXXXXXX
##-###	OnaB 20	M/F	XX	V#	XXXXXXXXXXXXXXXX

M=Male, F=Female

Version 1.1 31-May-2023 Confidential Page 24/58

Table 14.1.4 Subject Disposition per Visit

Disposition of Subjects at	PraB 40	OnaB 20	PraB 20
each Study Visit	(n = xx)	$(\mathbf{n} = \mathbf{x}\mathbf{x})$	$(\mathbf{n} = \mathbf{x}\mathbf{x})$
N	XX	XX	XX
V1 (screening)	xx (xx.x%)	xx(xx.x%)	xx(xx.x%)
V2 (pre-Tx)	xx(xx.x%)	xx(xx.x%)	xx (xx.x%)
V3 (48hr)	xx(xx.x%)	xx(xx.x%)	xx(xx.x%)
V4 (D7; phone f/u)	xx(xx.x%)	xx(xx.x%)	xx (xx.x%)
V5 (D30)	xx (xx.x%)	xx (xx.x%)	xx(xx.x%)
V6 (D60)	xx(xx.x%)	xx(xx.x%)	xx(xx.x%)
	xx(xx.x%)	xx(xx.x%)	xx (xx.x%)
	xx (xx.x%)	xx (xx.x%)	xx (xx.x%)
V16 (D365)	xx (xx.x%)	xx (xx.x%)	xx (xx.x%)

Number of subjects (% in parenthesis)

Table 14.1.5 Study Dates

FPFV	LPFV	LPLV	Enrollment Duration	Study Duration
dd-mmm-yyyy	dd-mmm-yyyy	dd-mmm-yyyy	XXX	XXX

FPFV= First Patient First Visit, LPFV= Last Patient First Visit, LPLV= Last Patient Last Visit. Enrollment duration=FPFV-LPFV+1, Study duration=FPFV-LPLV+1

Confidential Page 25/58

14.2 Demographic, Con-Med, Study Treatment Details

14.2.1 Demographics

Table 14.2.1.1 Demographics

Demographics		PraB 40	OnaB 20	PraB 20
		$(\mathbf{n} = \mathbf{x}\mathbf{x})$	(n = xx)	(n = xx)
Age	N	XX	xx	XX
	$Mean \pm SD$	$xx.x \pm xx.x [xx.x,xx.x]$	$xx.x \pm xx.x [xx.x,xx.x]$	$xx.x \pm xx.x [xx.x,xx.x]$
	Median (P25, P75)	xx.x(xx.x, xx.x)	xx.x(xx.x, xx.x)	xx.x(xx.x, xx.x)
	Min, Max	XX, XX	xx, xx	XX, XX
	Missing values	XX	xx	XX
BMI	N	XX	xx	XX
	$Mean \pm SD$	$xx.x \pm xx.x [xx.x,xx.x]$	$xx.x \pm xx.x [xx.x,xx.x]$	$xx.x \pm xx.x [xx.x,xx.x]$
	Median (P25, P75)	xx.x (xx.x, xx.x)	xx.x (xx.x, xx.x)	xx.x (xx.x, xx.x)
	Min, Max	XX, XX	xx, xx	XX, XX
	Missing values	XX	xx	XX
Gender	N	XX	xx	xx
	Male	xx (xx.x%)	xx (xx.x%)	xx (xx.x%)
	Female	xx (xx.x%)	xx (xx.x%)	xx(xx.x%)
	Missing values	XX	xx	XX
Race	N	XX	xx	xx
	American Indian or Alaska Native	xx (xx.x%)	xx (xx.x%)	xx (xx.x%)
	Asian	xx (xx.x%)	xx (xx.x%)	xx (xx.x%)
	Black or African American	xx (xx.x%)	xx (xx.x%)	xx (xx.x%)
	Caucasian	xx (xx.x%)	xx (xx.x%)	xx (xx.x%)
	Hawaiian / Pacific Islander	xx (xx.x%)	xx (xx.x%)	xx (xx.x%)
	Other	xx (xx.x%)	xx (xx.x%)	xx(xx.x%)
	Missing values	XX	xx	XX
Ethnicity	N	XX	XX	XX
	Hispanic	xx (xx.x%)	xx (xx.x%)	xx (xx.x%)
	Non-Hispanic	xx (xx.x%)	xx (xx.x%)	xx (xx.x%)
	Missing values	XX	XX	XX
Baseline GLS	N	XX	xx	XX
	Mean \pm SD	$xx.x \pm xx.x [xx.x,xx.x]$	$xx.x \pm xx.x [xx.x,xx.x]$	$xx.x \pm xx.x [xx.x,xx.x]$
	Median (P25, P75)	xx.x (xx.x, xx.x)	xx.x (xx.x, xx.x)	xx.x (xx.x, xx.x)
	Moderate (2)	xx (xx.x%)	xx (xx.x%)	xx (xx.x%)
	Severe (3)	xx (xx.x%)	xx (xx.x%)	xx(xx.x%)

95% CI [xx.x,xx.x], Mean ± standard deviation. Number of subjects (% in parenthesis).

14.2.2 Inclusion / Exclusion Criteria

Table 14.2.2.1 Inclusion Criteria

[figure not shown]
Inclusion Criteria		(n = xx)
Inclusion 1	No	xx (xx.x%)
	Yes	xx (xx.x%)
Inclusion 2	No	xx (xx.x%)
	Yes	xx (xx.x%)
Inclusion 3	No	xx (xx.x%)
	Yes	xx (xx.x%)
	No	xx (xx.x%)
	Yes	xx (xx.x%)
	No	xx (xx.x%)
	Yes	xx (xx.x%)
Inclusion 6	No	xx (xx.x%)
	Yes	xx (xx.x%)

Number of subjects (% in parenthesis).

Table 14.2.2.2 Exclusion Criteria

Exclusion Criteria		(n = xx)
Exclusion 1	No	xx (xx.x%)
	Yes	xx (xx.x%)
Exclusion 2	No	xx (xx.x%)
	Yes	xx (xx.x%)
Exclusion 3	No	xx (xx.x%)
	Yes	xx (xx.x%)
	No	xx (xx.x%)
	Yes	xx (xx.x%)
	No	xx (xx.x%)
	Yes	xx(xx.x%)
	No	xx (xx.x%)
	Yes	xx (xx.x%)
Exclusion 22	No	xx (xx.x%)
	Yes	xx (xx.x%)

Number of subjects (% in parenthesis).

Confidential Page 27/58

14.2.3 Medical / Surgical History

} evolus™

Table 14.2.3.1 Medical / Surgical History

	PraB 40	OnaB 20	PraB 20
Medical / Surgical History	(n = xx)	(n = xx)	(n = xx)
Blood and lymphatic system disorders	xx (xx.x%) [xx.x,xx.x]	xx (xx.x%) [xx.x,xx.x]	xx (xx.x%) [xx.x,xx.x]
2. Cardiac/Vascular disorders	xx (xx.x%) [xx.x,xx.x]	xx (xx.x%) [xx.x,xx.x]	xx (xx.x%) [xx.x,xx.x]
3. Eye/Ear and labyrinth disorders	xx (xx.x%) [xx.x,xx.x]	xx (xx.x%) [xx.x,xx.x]	xx (xx.x%) [xx.x,xx.x]
4. Endocrine disorders	xx (xx.x%) [xx.x,xx.x]	xx (xx.x%) [xx.x,xx.x]	xx (xx.x%) [xx.x,xx.x]
5. Gastrointestinal/Hepatobiliary disorders	xx (xx.x%) [xx.x,xx.x]	xx (xx.x%) [xx.x,xx.x]	xx (xx.x%) [xx.x,xx.x]
6. Gen. disorders and administration site conditions	xx (xx.x%) [xx.x,xx.x]	xx (xx.x%) [xx.x,xx.x]	xx (xx.x%) [xx.x,xx.x]
7. Immune system disorders	xx (xx.x%) [xx.x,xx.x]	xx (xx.x%) [xx.x,xx.x]	xx (xx.x%) [xx.x,xx.x]
8. Infections and infestations	xx (xx.x%) [xx.x,xx.x]	xx (xx.x%) [xx.x,xx.x]	xx (xx.x%) [xx.x,xx.x]
9. Injury, poisoning and procedural complications	xx (xx.x%) [xx.x,xx.x]	xx (xx.x%) [xx.x,xx.x]	xx (xx.x%) [xx.x,xx.x]
10. Metabolism and nutrition disorders	xx (xx.x%) [xx.x,xx.x]	xx (xx.x%) [xx.x,xx.x]	xx (xx.x%) [xx.x,xx.x]
11. Musculoskel. and connective tissue disorders	xx (xx.x%) [xx.x,xx.x]	xx (xx.x%) [xx.x,xx.x]	xx (xx.x%) [xx.x,xx.x]
12. Neoplasms benign, malignant and unspecified	xx (xx.x%) [xx.x,xx.x]	xx (xx.x%) [xx.x,xx.x]	xx (xx.x%) [xx.x,xx.x]
13. Nervous system disorders	xx (xx.x%) [xx.x,xx.x]	xx (xx.x%) [xx.x,xx.x]	xx (xx.x%) [xx.x,xx.x]
14. Psychiatric disorders	xx (xx.x%) [xx.x,xx.x]	xx (xx.x%) [xx.x,xx.x]	xx (xx.x%) [xx.x,xx.x]
15. Renal and urinary disorders	xx (xx.x%) [xx.x,xx.x]	xx (xx.x%) [xx.x,xx.x]	xx (xx.x%) [xx.x,xx.x]
16. Reproductive system and breast disorders	xx (xx.x%) [xx.x,xx.x]	xx (xx.x%) [xx.x,xx.x]	xx (xx.x%) [xx.x,xx.x]
17. Resp., thoracic and mediastinal disorders	xx (xx.x%) [xx.x,xx.x]	xx (xx.x%) [xx.x,xx.x]	xx (xx.x%) [xx.x,xx.x]
18. Skin and subcutaneous tissue disorders	xx (xx.x%) [xx.x,xx.x]	xx (xx.x%) [xx.x,xx.x]	xx (xx.x%) [xx.x,xx.x]
19. Surgical and medical procedures	xx (xx.x%) [xx.x,xx.x]	xx (xx.x%) [xx.x,xx.x]	xx (xx.x%) [xx.x,xx.x]
20. Allergies	xx (xx.x%) [xx.x,xx.x]	xx (xx.x%) [xx.x,xx.x]	xx (xx.x%) [xx.x,xx.x]
21. Other	xx (xx.x%) [xx.x,xx.x]	xx (xx.x%) [xx.x,xx.x]	xx (xx.x%) [xx.x,xx.x]

Number of subjects (% in parenthesis).

95% CI [xx.x,xx.x]

14.2.4 Concomitant Medications/Treatment

Table 14.2.4.1 Concomitant Medications/Treatment

	PraB 40	OnaB 20	PraB 20
Concomitant Medication/Treatment	$(\mathbf{n} = \mathbf{x}\mathbf{x})$	$(\mathbf{n} = \mathbf{x}\mathbf{x})$	(n = xx)
xxxxxxxxxxxxxxxxxxxxxxxxxxxx	xx (xx.x%) [xx.x,xx.x]	xx (xx.x%) [xx.x,xx.x]	xx (xx.x%) [xx.x,xx.x]
xxxxxxxxxxxxxxxxxxxxxxxxxxxx	xx (xx.x%) [xx.x,xx.x]	xx (xx.x%) [xx.x,xx.x]	xx (xx.x%) [xx.x,xx.x]
xxxxxxxxxxxxxxxxxxxxxxxxxxxx	xx (xx.x%) [xx.x,xx.x]	xx (xx.x%) [xx.x,xx.x]	xx (xx.x%) [xx.x,xx.x]
XXXXXXXXXXXXXXXXXXXXXXXXXXXXXXXXXXXXXXX	xx (xx.x%) [xx.x,xx.x]	xx (xx.x%) [xx.x,xx.x]	xx (xx.x%) [xx.x,xx.x]
XXXXXXXXXXXXXXXXXXXXXXXXXXXXXXXXXXXXXXX	xx (xx.x%) [xx.x,xx.x]	xx (xx.x%) [xx.x,xx.x]	xx (xx.x%) [xx.x,xx.x]
xxxxxxxxxxxxxxxxxxxxxxxxxxxxx	xx (xx.x%) [xx.x,xx.x]	xx (xx.x%) [xx.x,xx.x]	xx (xx.x%) [xx.x,xx.x]
XXXXXXXXXXXXXXXXXXXXXXXXXXXXXXXXXXXXXXX	xx (xx.x%) [xx.x,xx.x]	xx (xx.x%) [xx.x,xx.x]	xx (xx.x%) [xx.x,xx.x]
XXXXXXXXXXXXXXXXXXXXXXXXXXXXXXXXXXXXXXX	xx (xx.x%) [xx.x,xx.x]	xx (xx.x%) [xx.x,xx.x]	xx (xx.x%) [xx.x,xx.x]
XXXXXXXXXXXXXXXXXXXXXXXXXXXXXXXXXXXXXXX	xx (xx.x%) [xx.x,xx.x]	xx (xx.x%) [xx.x,xx.x]	xx (xx.x%) [xx.x,xx.x]
XXXXXXXXXXXXXXXXXXXXXXXXXXXXXXXXXXXXXXX	xx (xx.x%) [xx.x,xx.x]	xx (xx.x%) [xx.x,xx.x]	xx (xx.x%) [xx.x,xx.x]
XXXXXXXXXXXXXXXXXXXXXXXXXXXXXXXXXXXXXXX	xx (xx.x%) [xx.x,xx.x]	xx (xx.x%) [xx.x,xx.x]	xx (xx.x%) [xx.x,xx.x]
XXXXXXXXXXXXXXXXXXXXXXXXXXXXXXXXXXXXXXX	xx (xx.x%) [xx.x,xx.x]	xx (xx.x%) [xx.x,xx.x]	xx (xx.x%) [xx.x,xx.x]
xxxxxxxxxxxxxxxxxxxxxxxxxxxxx	xx (xx.x%) [xx.x,xx.x]	xx (xx.x%) [xx.x,xx.x]	xx (xx.x%) [xx.x,xx.x]
XXXXXXXXXXXXXXXXXXXXXXXXXXXXXXXXXXXXXXX	xx (xx.x%) [xx.x,xx.x]	xx (xx.x%) [xx.x,xx.x]	xx (xx.x%) [xx.x,xx.x]

Number of subjects (% in parenthesis).

95% CI [xx.x,xx.x]

Confidential Page 28/58

14.3 Efficacy Response Data

14.3.1 Primary Effectiveness Endpoint - Duration of Effect

Table 14.3.1.1 Duration of Effect (Investigator; Regardless of Responder Status; PraB 40 vs PraB 20)

GLS (Investigator) Duration of Effect	PraB 40	PraB 20
(Return to Baseline GLS score)	$(\mathbf{n} = \mathbf{x}\mathbf{x})$	$(\mathbf{n} = \mathbf{x}\mathbf{x})$
Subject Status, n (%)		
Returned to BL (event)	xx (xx%)	xx (xx%)
Censored	xx (xx%)	xx (xx%)
Kaplan-Meier Estimates for Return to BL		
1 st Quartile, (95% CI)	x.x(x.x, x.x)	x.x(x.x, x.x)
Median, (95% CI)	x.x(x.x, x.x)	x.x(x.x, x.x)
3 rd Quartile, (95% CI)	x.x(x.x, x.x)	x.x(x.x, x.x)
Adjusted Hazard Ratio (95% CI)	x.xx (x.:	xx, x.xx)
Stratified Log-Rank p-value	p <x.< td="">xxxx	</x.<>	xxxx
Unadjusted Hazard Ratio (95% CI)	zard Ratio (95% CI) x.xx (x.xx, x.xx)	
Unstratified Log-Rank p-value	p <x.xxxx< td=""></x.xxxx<>	

Data for all subjects regardless of Responder status

Duration of effect in days, calculated from Visit 2 (Treatment Day) to when subject returns to Baseline GLS score Responder = At least 1-Point improvement in GLS (max frown)

Version 1.1 31-May-2023

Confidential Page 29/58

14.3.2 Secondary Effectiveness Endpoints – Duration of Effect

Table 14.3.2.1 Duration of Effect (Investigator; Regardless of Responder Status; PraB vs OnaB)

GLS (Investigator) Duration of Effect	PraB 40	OnaB 20	PraB 20	OnaB 20
(Return to Baseline GLS score)	$(\mathbf{n} = \mathbf{x}\mathbf{x})$	$(\mathbf{n} = \mathbf{x}\mathbf{x})$	$(\mathbf{n} = \mathbf{x}\mathbf{x})$	$(\mathbf{n} = \mathbf{x}\mathbf{x})$
Subject Status, n (%)				
Returned to BL (event)	xx (xx%)	xx (xx%)	xx (xx%)	xx (xx%)
Censored	xx (xx%)	xx (xx%)	xx (xx%)	xx (xx%)
Kaplan-Meier Estimates for Return to B	L			
1 st Quartile, (95% CI)	x.x(x.x, x.x)	x.x(x.x, x.x)	x.x(x.x, x.x)	x.x(x.x, x.x)
Median, (95% CI)	x.x(x.x, x.x)	x.x(x.x, x.x)	x.x(x.x, x.x)	x.x(x.x, x.x)
3 rd Quartile, (95% CI)	x.x(x.x, x.x)	x.x(x.x, x.x)	x.x(x.x, x.x)	x.x(x.x, x.x)
Adjusted Hazard Ratio (95% CI)	x.xx (x.xx,	, x.xx)	x.xx (x.xx, x.xx)	
Stratified Log-Rank p-value	p <x.xx< td="">xx	p<x.xxxx< td=""></x.xxxx<>	</x.xx<>	xx	p <x.xxxx< td=""></x.xxxx<>	
Unadjusted Hazard Ratio (95% CI)	x.xx (x.xx,	, x.xx)	x.xx (x.xx, x.xx)	
Unstratified Log-Rank p-value	p <x.xx< td="">xx	p<x.xxxx< td=""></x.xxxx<>	</x.xx<>	xx	p <x.xxxx< td=""></x.xxxx<>	

Data for all subjects regardless of Responder status

Duration of effect in days, calculated from Visit 2 (Treatment Day) to when subject returns to Baseline GLS score Responder = At least 1-Point improvement in GLS (max frown)

Version 1.1 31-May-2023 Confidential Page 30/58

Table 14.3.2.2 Duration of Effect (Subject; Regardless of Responder Status)

GLS (Subject) Duration of Effect (Return to Baseline GLS score)	PraB 40 (n = xx)	PraB 20 (n = xx)	PraB 40 (n = xx)	OnaB 20 (n = xx)	PraB 20 (n = xx)	OnaB 20 (n = xx)
Subject Status, n (%)						
Returned to BL (event)	xx (xx%)	xx (xx%)	xx (xx%)	xx (xx%)	xx (xx%)	xx (xx%)
Censored	xx (xx%)	xx (xx%)	xx (xx%)	xx (xx%)	xx (xx%)	xx (xx%)
Kaplan-Meier Estimates for Return to B	BL					
1 st Quartile, (95% CI)	x.x(x.x, x.x)	x.x(x.x, x.x)	x.x(x.x, x.x)	x.x(x.x, x.x)	x.x(x.x, x.x)	x.x(x.x, x.x)
Median, (95% CI)	x.x(x.x, x.x)	x.x(x.x, x.x)	x.x(x.x, x.x)	x.x(x.x, x.x)	x.x(x.x, x.x)	x.x(x.x, x.x)
3 rd Quartile, (95% CI)	x.x(x.x, x.x)	x.x(x.x, x.x)	x.x(x.x, x.x)	x.x(x.x, x.x)	x.x(x.x, x.x)	x.x(x.x, x.x)
Adjusted Hazard Ratio (95% CI)	x.xx (x.xx,	, x.xx)	x.xx (x.xx	, x.xx)	x.xx (x.xx,	x.xx)
Stratified Log-Rank p-value	p <x.xx< td="">xx	p<x.xx< td="">xx	p<x.xx< td="">XX	</x.xx<>	</x.xx<>	</x.xx<>	xx	p <x.xx< td="">xx	p<x.xx< td="">XX	</x.xx<>	</x.xx<>	xx	p <x.xx< td="">XX	</x.xx<>	XX
Unadjusted Hazard Ratio (95% CI)	x.xx (x.xx,	, x.xx)	x.xx (x.xx, x.xx) x.xx (x.xx, x.x		x.xx)	
Unstratified Log-Rank p-value	p <x.xx< td="">xx	p<x.xxxx< td="">p<x.xx< td="">xx	</x.xx<>	</x.xxxx<>	</x.xx<>	xx	p <x.xxxx< td="">p<x.xx< td="">xx	</x.xx<>	</x.xxxx<>		p <x.xx< td="">xx	</x.xx<>	xx

Data for all subjects regardless of Responder status

Duration of effect in days, calculated from Visit 2 (Treatment Day) to when subject returns to Baseline GLS score Responder = At least 1-Point improvement in GLS (max frown)

Version 1.1 31-May-2023 Confidential Page 31/58

Table 14.3.2.3 Duration of Effect for GAIS Responders (Investigator; Score of 2 or 1 at Day 30)

GAIS (Investigator) Duration of Effect (Return to Baseline GAIS score)	PraB 40 (n = xx)	PraB 20 (n = xx)	PraB 40 (n = xx)	OnaB 20 (n = xx)	PraB 20 (n = xx)	OnaB 20 (n = xx)
Subject Status, n (%)						
Returned to BL (event)	xx (xx%)	xx (xx%)	xx (xx%)	xx (xx%)	xx (xx%)	xx (xx%)
Censored	xx (xx%)	xx (xx%)	xx (xx%)	xx (xx%)	xx (xx%)	xx (xx%)
Kaplan-Meier Estimates for Return to BL						
1 st Quartile, (95% CI)	x.x(x.x, x.x)	x.x(x.x, x.x)	x.x(x.x, x.x)	x.x(x.x, x.x)	x.x(x.x, x.x)	x.x(x.x, x.x)
Median, (95% CI)	x.x(x.x, x.x)	x.x(x.x, x.x)	x.x(x.x, x.x)	x.x(x.x, x.x)	x.x(x.x, x.x)	x.x(x.x, x.x)
3 rd Quartile, (95% CI)	x.x(x.x, x.x)	x.x(x.x, x.x)	x.x(x.x, x.x)	x.x(x.x, x.x)	x.x(x.x, x.x)	x.x(x.x, x.x)
Adjusted Hazard Ratio (95% CI)	x.xx (x.xx, x.xx)		x.xx (x.xx, x.xx)		x.xx (x.xx, x.xx)	
Stratified Log-Rank p-value	p <x.xxxx< td="">p<x.xxxx< td="">p<x.xxxx< td=""></x.xxxx<>	</x.xxxx<>	</x.xxxx<>		p <x.xxxx< td="">p<x.xxxx< td=""></x.xxxx<>	</x.xxxx<>		p <x.xxxx< td=""></x.xxxx<>	
Unadjusted Hazard Ratio (95% CI)	x.xx (x.xx, x.xx)		x.xx (x.xx, x.xx)		x.xx (x.xx, x.xx)	
Unstratified Log-Rank p-value	p <x.xxxx< td="">p<x.xxxx< td="">p<x.xxxx< td=""></x.xxxx<>	</x.xxxx<>	</x.xxxx<>		p <x.xxxx< td="">p<x.xxxx< td=""></x.xxxx<>	</x.xxxx<>		p <x.xxxx< td=""></x.xxxx<>	

Data for subjects deemed Responder on or before Visit 5 (Day 30)

 $\label{lem:condition} \textit{Duration of effect in days, calculated from Visit 2 (Treatment Day) to when subject returns to Baseline GAIS score} \\ \textit{Responder} = \textit{GAIS score of 2 or 1} \\$

Version 1.1 31-May-2023

Confidential Page 32/58

Table 14.3.2.4 Duration of Effect for GAIS Responders (Subject; Score of 2 or 1 at Day 30)

GAIS (Subject) Duration of Effect	PraB 40	PraB 20	PraB 40	OnaB 20	PraB 20	OnaB 20
(Return to Baseline GAIS score)	$(\mathbf{n} = \mathbf{x}\mathbf{x})$	$(\mathbf{n} = \mathbf{x}\mathbf{x})$	$(\mathbf{n} = \mathbf{x}\mathbf{x})$	$(\mathbf{n} = \mathbf{x}\mathbf{x})$	$(\mathbf{n} = \mathbf{x}\mathbf{x})$	$(\mathbf{n} = \mathbf{x}\mathbf{x})$
Subject Status, n (%)						
Returned to BL (event)	xx (xx%)	xx (xx%)	xx (xx%)	xx (xx%)	xx (xx%)	xx (xx%)
Censored	xx (xx%)	xx (xx%)	xx (xx%)	xx (xx%)	xx (xx%)	xx (xx%)
Kaplan-Meier Estimates for Return to B	L					
1 st Quartile, (95% CI)	x.x(x.x, x.x)	x.x(x.x, x.x)	x.x(x.x, x.x)	x.x(x.x, x.x)	x.x(x.x, x.x)	x.x(x.x, x.x)
Median, (95% CI)	x.x(x.x, x.x)	x.x(x.x, x.x)	x.x(x.x, x.x)	x.x(x.x, x.x)	x.x(x.x, x.x)	x.x(x.x, x.x)
3 rd Quartile, (95% CI)	x.x(x.x, x.x)	x.x(x.x, x.x)	x.x(x.x, x.x)	x.x(x.x, x.x)	x.x(x.x, x.x)	x.x(x.x, x.x)
Adjusted Hazard Ratio (95% CI)	x.xx (x.xx, x.xx)		x.xx (x.xx, x.xx)		x.xx (x.xx, x.xx)	
Stratified Log-Rank p-value	p <x.xxxx< td="">p<x.xxxx< td="">p<x.xxxx< td=""></x.xxxx<>	</x.xxxx<>	</x.xxxx<>		p <x.xxxx< td="">p<x.xxxx< td=""></x.xxxx<>	</x.xxxx<>		p <x.xxxx< td=""></x.xxxx<>	
Unadjusted Hazard Ratio (95% CI)	x.xx (x.xx, x.xx)		x.xx (x.xx, x.xx)		x.xx (x.xx, x.xx)	
Unstratified Log-Rank p-value	p <x.xxxx< td="">p<x.xxxx< td="">p<x.xxxx< td=""></x.xxxx<>	</x.xxxx<>	</x.xxxx<>		p <x.xxxx< td="">p<x.xxxx< td=""></x.xxxx<>	</x.xxxx<>		p <x.xxxx< td=""></x.xxxx<>	

Data for subjects deemed Responder on or before Visit 5 (Day 30)

 $\label{lem:condition} \textit{Duration of effect in days, calculated from Visit 2 (Treatment Day) to when subject returns to Baseline GAIS score} \\ \textit{Responder} = \textit{GAIS score of 2 or 1} \\$

Version 1.1 31-May-2023 Confidential Page 33/58

Table 14.3.2.5 Duration of Effect for SSS Responders (Subject; Score of 2 or 1 at Day 30)

SSS (Subject) Duration of Effect	PraB 40	PraB 20	PraB 40	OnaB 20	PraB 20	OnaB 20
(Return to Baseline SSS score)	$(\mathbf{n} = \mathbf{x}\mathbf{x})$	$(\mathbf{n} = \mathbf{x}\mathbf{x})$	$(\mathbf{n} = \mathbf{x}\mathbf{x})$	$(\mathbf{n} = \mathbf{x}\mathbf{x})$	$(\mathbf{n} = \mathbf{x}\mathbf{x})$	$(\mathbf{n} = \mathbf{x}\mathbf{x})$
Subject Status, n (%)	()	(22 3332)	(= ::::)	()	()	()
Returned to BL (event)	xx (xx%)	xx (xx%)	xx (xx%)	xx (xx%)	xx (xx%)	xx (xx%)
Censored	xx (xx%)	xx (xx%)	xx (xx%)	xx (xx%)	xx (xx%)	xx (xx%)
Kaplan-Meier Estimates for Return to B	BL					
1 st Quartile, (95% CI)	x.x(x.x, x.x)	x.x(x.x, x.x)	x.x (x.x, x.x)	x.x(x.x, x.x)	x.x(x.x, x.x)	x.x(x.x, x.x)
Median, (95% CI)	x.x(x.x, x.x)	x.x(x.x, x.x)	x.x(x.x, x.x)	x.x(x.x, x.x)	x.x(x.x, x.x)	x.x(x.x, x.x)
3 rd Quartile, (95% CI)	x.x(x.x, x.x)	x.x(x.x, x.x)	x.x(x.x, x.x)	x.x(x.x, x.x)	x.x(x.x, x.x)	x.x(x.x, x.x)
Adjusted Hazard Ratio (95% CI)	x.xx (x.xx, x.xx)		x.xx (x.xx, x.xx)		x.xx (x.xx, x.xx)	
Stratified Log-Rank p-value	p <x.xxxx< td="">p<x.xxxx< td="">p<x.xxxx< td=""></x.xxxx<>	</x.xxxx<>	</x.xxxx<>		p <x.xxxx< td="">p<x.xxxx< td=""></x.xxxx<>	</x.xxxx<>		p <x.xxxx< td=""></x.xxxx<>	
Unadjusted Hazard Ratio (95% CI)	x.xx (x.xx, x.xx)		x.xx (x.xx, x.xx)		x.xx (x.xx, x.xx)	
Unstratified Log-Rank p-value	p <x.xxxx< td="">p<x.xxxx< td="">p<x.xxxx< td=""></x.xxxx<>	</x.xxxx<>	</x.xxxx<>		p <x.xxxx< td="">p<x.xxxx< td=""></x.xxxx<>	</x.xxxx<>		p <x.xxxx< td=""></x.xxxx<>	

Data for subjects deemed Responder on or before Visit 5 (Day 30)

 $\label{eq:continuous} \textit{Duration of effect in days, calculated from Visit 2 (Treatment Day) to when subject returns to Baseline SSS score} \\ \textit{Responder} = SSS score of 2 \text{ or } 1$

Confidential Page 34/58

